3.6.2. Laboratory Data

- *Clinically significant abnormal laboratory parameters.*
- Clinical laboratory values and change from baseline at Weeks 12 and 24.
- Clinical laboratory values and change from baseline and randomization at Weeks 36 and 48.

4. ANALYSIS SETS

4.1. Full Analysis Set

There are two full analysis sets, one is for open-label run-in phase and one is for double-blind MTX withdrawal phase.

- **Open-Label Period Full Analysis Set (FAS-OL)**

FAS-OL includes all subjects who received at least one dose of tofacitinib MR 11mg plus MTX during open-label phase.

- **Double-Blind Period Full Analysis Set (FAS-DB)**

FAS-DB includes all subjects who received at least one dose of tofacitinib MR 11mg plus MTX during the open-label run-in phase, and were randomized and received at least one dose of the randomized investigational drug regimen (tofacitinib MR 11mg with MTX or tofacitinib MR 11mg with placebo for MTX) during the blinded MTX withdrawal phase.

A randomized but not treated subject, or treated but not randomized subject during MTX withdrawal phase will be excluded from FAS-DB.

A subjects who was randomized but took incorrect treatment during MTX withdrawal phase will be reported under the randomized treatment group for all efficacy analyses.

4.2. Per Protocol Analysis Set

The Per Protocol Analysis Set (PPAS) will be a subset of subjects from FAS-DB. Subjects who had a protocol deviation during the blinded MTX withdrawal period thought to affect the efficacy analysis will be excluded from the Per Protocol efficacy analysis. The PPAS will be defined for double-blind period only. Note that the protocol deviation may have occurred during open-label period. Protocol deviations will be assessed by the study team prior to unblinding the study. This list of subjects along with exclusions from per protocol analyses will be put into the trial master file.

4.3. Safety Analysis Set

There are three safety analysis sets, two for two study phases (open-label run-in phase and double-blind MTX withdrawal phase) and one for overall study period.

- **Open-Label Run-in Phase Safety Analysis Set (Safety-OL)**

Safety-OL will include all subjects who received at least one dose of tofacitinib MR 11mg QD plus MTX during open-label run-in period. It is same as FAS-OL.

- **Double-Blind MTX Withdrawal Phase Safety Analysis Set (Safety-DB)**

Safety-DB will include all subjects who received at least one dose of study drug (tofacitinib MR 11mg QD with blinded MTX or tofacitinib MR 11mg QD with blinded matching placebo for MTX) during double-blind MTX withdrawal phase.

- **Overall Study Safety Analysis Set (Safety-All)**

Safety-All consists of all subjects who received at least one dose of study drug during the study.

4.4. Other Analysis Sets

N/A.

5. GENERAL METHODOLOGY AND CONVENTIONS

5.1. Hypotheses and Decision Rules

The primary analysis will be a non-inferiority test to show that tofacitinib MR 11mg QD monotherapy is not less effective (non-inferior) than tofacitinib MR 11mg QD with MTX within the margin of non-inferiority set at 0.6 (ie, the difference in mean change from randomization in DAS28-4 (ESR) between the two arms). If the upper bound of the 95% two-sided confidence interval (CI) for the difference (tofacitinib monotherapy arm minus tofacitinib with MTX arm) in change from randomization to Week 48 in DAS 28-4 (ESR)

between the two arms is lower than 0.6, then tofacitinib monotherapy will be declared to be non-inferior to the tofacitinib with continued MTX treatment.

5.2. General Methods

In general, number and percent will be presented for categorical variables. Number, mean, standard deviation (standard error of the mean), minimum, 1st, 2nd and 3rd quartiles and maximum will be presented for continuous variables. In addition, graphics will be used to present the data.

The data will be described and analyzed by study phase.

Note that the primary statistical hypotheses are based on data solely from blinded MTX withdrawal phase. Analyses of endpoints during open-label run-in phase are intended to be descriptive in nature.

5.2.1. Analyses for Binary Data

Binary endpoints in the blinded MTX withdrawal phase will be analyzed using the normal approximation for the difference in binomial proportions. The estimated treatment difference, the associated 95% CI and p-value will be presented.

Binary endpoints in the open-label run-in phase will be summarized using number, percentage and 95% CI of percentage.

5.2.2. Analyses for Continuous Data

The primary endpoint of change from randomization in DAS28-4(ESR) at Week 48 will be analyzed using a linear mixed-effect model of repeated measures (MMRM) that includes the fixed effects of treatment, visit, treatment-by-visit interaction, prior use of a biological DMARD, and baseline DAS28-4 (ESR) value as a covariate. Within-subject variability will be accounted for using a random effect with an unstructured covariance matrix. The least square (LS) mean of treatment, and LS mean difference and the associated 95% confidence interval (CI) will be presented.

If the model with an unstructured covariance matrix doesn't converge or is unstable, 1st order autoregressive will be fitted instead. If the convergence problem persists, compound symmetry will be used.

Continuous secondary endpoints in the blinded MTX withdrawal phase will be analyzed using similar methods as the primary endpoint.

Continuous endpoints in the open-label run-in phase will be descriptively summarized using number, mean, standard deviation (standard error of the mean), minimum, 1st, 2nd and 3rd quartiles and maximum.

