3.2. Secondary Efficacy Endpoint(s)

- Change in the DAS28-4(ESR) from Week 24 to Week 36;
- Changes in the DAS28-4 (CRP), CDAI and SDAI, respectively, from Week 24 to Week 48 and from Week 24 to Week 36;
- LDA as assessed by DAS28-4(ESR) ≤ 3.2, DAS28-4(CRP) ≤ 3.2, CDAI ≤ 10 and SDAI ≤ 11, respectively, at Weeks 48 and 36;
- Remission as assessed by ACR-EULAR Boolean remission criteria, DAS28-4 (ESR) < 2.6, DAS28-4 (CRP) < 2.6, CDAI ≤ 2.8 and SDAI ≤ 3.3, respectively, at Weeks 48 and 36;
- ACR20, ACR 50, and ACR70 responses, respectively, at Weeks 48 and 36;

- Change in the HAQ-DI, the SF-36 (8 domain scores and 2 component scores), WPAI, EuroQol EQ-5D and the FACIT-Fatigue scale score, respectively, from Week 24 to Week 48 and from Week 24 to Week 36;
- HAQ-DI response (ie, decrease of at least 0.22) at Weeks 48 and 36.
- Note:
- For subjects entering the double-blind phase, the value at randomization (Week 24) for each endpoint is the last nonmissing observation before the first dose of study drug in double-blind phase.
- The baseline (Day 1) value for each endpoint is the last nonmissing observation before the first dose of study drug in open-label run-in phase.
- ACR20, ACR 50, ACR70, and HAQ-DI responses are relative to baseline (Day 1).

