5.3.2. DAS28-4(ESR), DAS28-4(CRP), CDAI, SDAI

DAS28-4(ESR) is a derived variable from 4 components. If any component is missing, DAS28-4(ESR) will be missing.

Above approach will also be used for DAS28-4(CRP), CDAI, SDAI.

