6.1.1.1. Primary Analysis

- Analysis time points: Week 48
- Analysis population: FAS-DB
- Analysis methodology: Change from randomization (at Week 24) will be analyzed using the MMRM (specified in [Section 5.2.2](#)).
- Covariate: Baseline of DAS28-4(ESR) and prior use of a bDMARD.
- Imputation for missing values: Observed data will be included in the MMRM model, the missing values will be handled in the model, where the values are assumed to be missing at random.
- Supporting objective and Decision rule: Primary Objective, upper bound of 95% CI of treatment difference < 0.6.

Reporting results:

- Raw data: The sample size, mean, standard deviation, median, minimum and maximum at randomization (Week 24) and post-randomization visits will be presented for each treatment arm.
- Change from randomization: The sample size, mean, standard deviation, median, minimum and maximum will be presented for each treatment arm. The LS means, 95% confidence interval for the LS means, difference between the LS means between treatment groups and the corresponding 95% CI, p-value will be presented.

Figures

- Line plots of the LS means (+/-SE) at Weeks 48 and 36 for two treatment groups.
- Plot of 95% CI of the LS mean difference between treatment groups at Weeks 48 and 36.

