6.1.1.2.2. Multiple Imputations

- Dependence Variable: Change in the DAS28-4(ESR) from Week 24 to Week 48
- Analysis population: FAS-DB
- Analysis time point: Week 48
- Analysis methodology: Change from Week 24 will be analyzed using the MMRM (specified in [Section 5.2.2](#)).
- Covariate: Baseline of DAS28-4(ESR) and prior use of a biological DMARD
- Imputation for missing values: multiple imputation (see [Section 5.3](#)).

Reporting results:

- Change from Week 24: The LS means, 95% confidence interval for the LS means, difference between the LS means between treatment groups and the corresponding 95% CI will be presented.
- Plot of 95% CI of the LS mean difference between treatment groups at Weeks 48 and 36.

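### As defined in the SAP, the primary model adjusts for the Day 1 DAS28-4(ESR) and never for the Week 24 score from which change is measured; adding the Week 24 score costs almost nothing

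*SAP*

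**What the plan says.** Protocol 9.3.1 defines the outcome as the DAS28-4(ESR) at a post-randomization visit minus the value at randomization. The model in Protocol 9.3.1 and SAP 5.2.2 has treatment, visit, their interaction, "prior use of a biological DMARD, and baseline DAS28-4 (ESR) value as a covariate". SAP 6.1.1.1 repeats "Covariate: Baseline of DAS28-4(ESR) and prior use of a bDMARD", as does the per-protocol analysis in 6.1.1.2.1. The multiple-imputation analysis in 6.1.1.2.2 has "Covariate: Baseline of DAS28-4(ESR) and prior use of a biological DMARD". The continuous secondary endpoints (SAP 6.2.2 and 6.2.3, Protocol 9.3.2) follow the same pattern, and the subgroup model in SAP 6.5 inherits 5.2.2.

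The term is defined in the note to SAP 3.2: "The baseline (Day 1) value for each endpoint is the last nonmissing observation before the first dose of study drug in open-label run-in phase". The same note defines a second quantity: "the value at randomization (Week 24) for each endpoint is the last nonmissing observation before the first dose of study drug in double-blind phase". SAP Appendix 1.2 gives the two separate rows with separate windows. SAP 3.6.2 uses both as distinct reference points: "Clinical laboratory values and change from baseline and randomization at Weeks 36 and 48". Protocol 9.2 and the visit names (Visit 1 Baseline, Visit 4 Randomization) keep them apart as well.

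**The concern.** When change is measured from Week 24, the Week 24 score is the natural pre-randomization covariate: regression to the mean ties it to the change. On the SAP's own definitions the model adjusts for a score taken 24 weeks earlier and omits this one. The design does not balance it either, since randomization is stratified only by prior biologic DMARD exposure (Protocol 4.3). Two things follow: the confidence interval compared with 0.6 may be wider than it need be, and a chance Week 24 difference between arms passes unadjusted into the estimate. These are two views of one effect. Neither biases the analysis or inflates type I error when data are complete.

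**Working it through.** **Reproducing the plan (Protocol 9.1).** Margin 0.6, SD 1.4, two-sided 5%, 90% power, true difference 0, 1:1 allocation. Per arm, n = 2 × 1.4² × (1.960 + 1.282)² / 0.6² = 114.4, so 115 (230 in total). With the t distribution, 115 per arm gives 89.9% and 116 gives 90.2%, so the stated 232 is reproduced. At 116 per arm, SE = 1.4 × √(2/116) = 0.184 and the normal-approximation power is Φ(0.6/0.184 − 1.96) = 90.4%.

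**Assumed inputs.** The documents give no Week 24 SD or correlations. Week 24 SD (s24): 0.6, 0.7, 0.8, 0.9, 1.0; low values are plausible because only subjects in CDAI low disease activity are randomized. Week 24–Week 48 correlation (r): 0.3, 0.4, 0.5. Day 1–Week 48 correlation (q): 0.2, 0.3, 0.4. Day 1–Week 24 correlation: 0.3. Day 1 SD scaled to 1. SD of change held at 1.4 (variance 1.96). This gives 45 cases.

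**Formulas.**
- s48 solves s24² + s48² − 2·r·s24·s48 = 1.96.
- Covariance of change with Day 1: c1 = q·s48 − 0.3·s24. With Week 24: c24 = r·s24·s48 − s24².
- Residual variance given Day 1: 1.96 − c1². Given Week 24 alone: 1.96 − c24²/s24². Given both: 1.96 − c′S⁻¹c, with c = (c1, c24) and S the covariance matrix of Day 1 and Week 24.
- SE = √(2v/116); half-width = 1.96·SE; power = Φ(0.6/SE − 1.96).

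**Three cases.**

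| s24, r, q | s48 | c1 | c24 | v, Day 1 | v, both | v, Week 24 alone | Cut, both vs Day 1 | Power, Day 1 → both |
|---|---|---|---|---|---|---|---|---|
| 0.8, 0.5, 0.2 (least gain) | 1.617 | 0.083 | 0.007 | 1.9531 | 1.9528 | 1.9599 | 0.02% | 90.5 → 90.5% |
| 0.8, 0.4, 0.3 | 1.513 | 0.214 | −0.156 | 1.914 | 1.841 | 1.922 | 3.8% | 91.0 → 92.0% |
| 1.0, 0.3, 0.4 (most gain) | 1.325 | 0.230 | −0.603 | 1.907 | 1.412 | 1.597 | 26.0% | 91.1 → 97.0% |

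**All 45 cases, both against Day 1 only.**
- Variance cut 0.02 to 26.0%, median 3.7%; below 6% in 29 cases; never negative.
- At s24 = 0.6 the cut is at most 5%, and at r = 0.5 at most 5.4%. Cuts of 20% or more need s24 = 1.0 with r = 0.3.
- Half-width 0.340–0.360 becomes 0.306–0.360; the narrowing is at most 0.05, median 0.007.
- Power 90.4–93.3% becomes 90.5–97.0%; median gain 1.0 point, largest 5.9.
- Effect of a one-SE Week 24 imbalance given Day 1, s24·√(1 − 0.3²)·√(2/116) = 0.075 to 0.125 units: multiplied by the Week 24 coefficient, it moves the Day 1-adjusted difference by 0.002 to 0.092 (median 0.035).
- Week 24 in place of Day 1: variance rises in 23 cases, by up to 10.5%.

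**Simulation.** In five cases of the Week 48 analysis with a prior-biologic term (complete data, 4,000 runs each), false non-inferiority at a true difference of 0.6 was 2.2–2.6% with Day 1 and 2.1–2.7% with both. In the worst case for cost, the mean SE went from 0.1840 to 0.1844.

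**Other assumptions.** Take equal unselected SDs, Week 24–Week 48 correlation 0.4–0.8 and the best 40% or 79% selected at Week 24. Week 24 then explains a further 5–28% of the variance beyond Day 1. In a simulated two-visit unstructured model (500 trials per setting, correlations 0.5 and 0.7) the SE fell from 0.183 to 0.169 and 0.176.

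**The case against.** **Baseline could mean Week 24.** The definition sits in a note under secondary endpoints, SAP 5.2.2 does not cite it, the outcome is change from randomization, and SAP 5.2 says "Note that the primary statistical hypotheses are based on data solely from blinded MTX withdrawal phase". A programmer could therefore use Week 24. That possibility stands, but the SAP 5.2 sentence does not redefine the term, and the note covers each endpoint. If the sponsor does mean Week 24, the text still says otherwise, and naming both values settles it.

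**The gain may be negligible.** This stands. In 23 of the 45 cases power rises by less than one point, and three of the five simulated cases show no real gain. The inputs are assumptions, and other inputs give other ranges.

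**The grid is not the specified model.** It treats Week 48 alone with complete normal data, whereas the plan fits Weeks 36 and 48 with data missing at random. The two-visit simulation goes part of the way to meeting this. Nothing was computed for the secondary endpoints.

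**Missing data are left out.** The statement that the present model is unbiased is limited to complete data. In an illustrative simulation with about 15% dropout, in the monotherapy arm only and depending on the Week 24 score, the Day 1 model was biased by about +0.05 and the model with both by −0.01 to +0.005. That favours the change. The imputation in SAP 5.3 draws only by treatment and time point, so it already ignores every covariate; the change does not make that worse.

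**Conclusion.** The point holds as a free improvement, not as a defect. In the visible text, the covariate is the Day 1 score and the Week 24 score enters no model. The planned 232 subjects and 90% power stand. The benefit of adding Week 24 runs from nothing to modest, and its size depends on a Week 24 SD and correlations that the documents do not give. What does not depend on the range chosen is the direction: with Day 1 retained, residual variance never rises, and the simulations show no type I inflation.

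**What to change.** Before unblinding, add the value at randomization (Week 24) of the endpoint being analysed as a covariate, entered as a main effect. Keep the existing covariate and label it baseline (Day 1). Do not swap one for the other. Make the change in SAP 5.2.2, 6.1.1.1, 6.1.1.2.1, 6.1.1.2.2, 6.2.2 and 6.2.3, in Protocol 9.3.1 and 9.3.2, and in the statistical methods of the Protocol Summary. SAP 6.5 follows from 5.2.2.

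The statistical cost is one degree of freedom; if Week 24 explains nothing, t-based power goes from 90.15% to 90.03%. Sample size, alpha, margin and endpoint are unchanged, and no new data are needed. No subject is lost, because a subject without a Week 24 score has no change score in any case: SAP 5.3.2 says "If any component is missing, DAS28-4(ESR) will be missing". The procedural cost is revised wording and, if the change counts as a major modification of the primary analysis under Protocol 9 and SAP 2, a protocol amendment.

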5.2.3. Analyses for Categorical Data

Categorical endpoints will be summarized using number and percentage.

5.3. Methods to Manage Missing Data

For continuous endpoints, missing values will not be imputed for descriptive statistics. For continuous endpoints in the blinded MTX withdrawal phase, the missing values post-randomization will be handled in a linear mixed-effect model with repeated measures for this continuous variable, where the values are assumed to be missing at random.

Multiple Imputation will be used for sensitivity analysis for DAS28-4(ESR) change from randomization (Week 24) in the double-blind phase. Imputed values will be sampled (or randomly drawn) from the normal distribution based on the observed mean and SD of non-missing data by treatment and time point and the full analysis will be conducted on the 'filled-in' (observed and imputed together) data multiple times (500 times). The final results will be presented as a summary of these multiple analyses.

In addition, missing values for safety endpoints will not be imputed.

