9.3. Efficacy Analysis

9.3.1. Analysis of the Primary Endpoint

The primary endpoint of change from randomization in DAS28-4(ESR) at Week 48 will be analyzed as a continuous variable using a linear mixed-effect model of repeated measures (MMRM) that includes the fixed effects of treatment, visit, treatment-by-visit interaction, prior use of a biological DMARD, and baseline DAS28-4 (ESR) value as a covariate. Within-subject variability will be accounted for using a random effect with an unstructured covariance matrix. Change from randomization at any visit post-randomization will be defined as the DAS28-4 (ESR) value at that visit minus the value at randomization.

The primary analysis will be a non-inferiority test to show that tofacitinib MR 11mg QD monotherapy is not less effective (non-inferior) than tofacitinib MR 11mg QD with MTX within the margin of non-inferiority set at 0.6 (ie, the difference in mean change from randomization in DAS28-4 (ESR) between the two arms). In other words, the change from randomization in DAS28-4(ESR) for the tofacitinib MR 11mg QD monotherapy arm may be less favorable than that for the tofacitinib MR 11mg QD with continued MTX arm by no more than 0.6. The estimated treatment difference and the associated 95% confidence interval (CI) will be presented. If the upper bound of the 95% two-sided CI for the difference (tofacitinib monotherapy arm minus tofacitinib with MTX arm) in change from randomization in DAS 28-4 (ESR) between the two arms is lower than 0.6, then tofacitinib monotherapy will be declared to be non-inferior to the tofacitinib with continued MTX treatment.

The analysis will be based on the Full Analysis Set (FAS), which is defined as those subjects who received at least one dose of tofacitinib plus MTX during the open label period and were randomized and received at least one dose of the randomized investigational drug (tofacitinib MR 11mg QD with placebo for MTX or tofacitinib MR 11mg QD with MTX) during the blinded MTX withdrawal period.

A robustness analysis based on a per-protocol analysis set will be performed. Sensitivity analyses using different methods of handling missing data will also be conducted; further details will be outlined in the SAP.

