6.1.1.2. Sensitivity/Robustness Analyses

To support the interpretation of the primary analysis the following analyses will be performed:

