6.1.1.2.1. Analysis for PPAS

- Dependent Variable: Change in the DAS28-4(ESR) from Week 24 to Week 48
- Analysis time points: Week 48
- Analysis population: PPAS
- Analysis methodology: Change from Week 24 will be analyzed using the MMRM (specified in [Section 5.2.2](#)).
- Covariate: Baseline of DAS28-4(ESR) and prior use of a bDMARD.
- Imputation for missing values: Observed data will be included in the MMRM model, the missing values will be handled in the model, where the values are assumed to be missing at random.
- Supporting objective and Decision rule: Primary Objective, upper bound of 95% CI of treatment difference <0.6.

Reporting results:

- Raw data: The sample size, mean, standard deviation, median, minimum and maximum at randomization (Week 24) and post-randomization visits will be presented for each treatment arm.

- Change from randomization: The sample size, mean, standard deviation, median, minimum and maximum will be presented for each treatment arm. The LS means, 95% confidence interval for the LS means, difference between the LS means between treatment groups, the corresponding 95% CI and p-value will be presented.

Figures

- Line plots of the LS means (+/-SE) at Weeks 48 and 36 for two treatment groups.
- Plot of 95% CI of the LS mean difference between treatment groups at Weeks 48 and 36.

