Appendix 1.2. Definition and Use of Visit Windows in Reporting

Visit windows will be used for efficacy variables, and for any safety displays that display by week.

If more than one observation from the same subject falls into the same visit window, the value closest to the targeted day will be used as the observation for that week. If two visits are equal distant from the Targeted Day in absolute value, the later visit should be used. All observations will, however, be included in the listings.

For endpoints derived from multiple components, eg, DAS28-4(ESR), each component will be windowed to select the value for analysis at a specific visit, and the value of the endpoint will then be derived. This means the component values may be from different visit dates that fall within the analysis window.

Subjects’ observations will be excluded from visit windows if the data was collected more than 7 days off study drug. (Safety analysis may follow Pfizer standard.)

Visit Label	Targeted Day	Analysis window for data sets
Open-Label Run-In Phase		
Baseline	Day 1	Last Observation up to and including First Dosing Date (no earlier than Day -90)
Week 6	Day 42	Days 2 – 63
Week 12	Day 84	If there is Week 6 visit such as lab tests: Days 64 – 126; If no Week 6 visit: Days 2 – 126
Week 24	Day 168	Day 127 – Discontinuation Day /Randomization Day (the earlier one)
Double-Blind Phase		
Randomization (Week 24)	Randomization Day	Last Observation up to and including First Dosing Date in Double-Blind Phase (no earlier than Day 127)
Week 36	Randomization Day + 84	Randomization Day + 1 – Randomization Day + 126
Week 48	Randomization Day + 168	Randomization Day + 127 –

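### The only missing-data sensitivity analysis of the primary endpoint returns the observed-case difference and tests no departure from missing at random

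*SAP*

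**What the plan says.** Protocol 9.3.1 promises that "Sensitivity analyses using different methods of handling missing data will also be conducted" and leaves the detail to the SAP. SAP 6.1.1.2 introduces its list with "To support the interpretation of the primary analysis the following analyses will be performed", and two analyses follow.

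- **Per-protocol set (SAP 6.1.1.2.1).** This refits the same MMRM, and "the missing values will be handled in the model, where the values are assumed to be missing at random". It changes the population, not the missing-data assumption.
- **Multiple imputation (SAP 6.1.1.2.2).** The entry reads "Imputation for missing values: multiple imputation" and refers to SAP 5.3, where values are "sampled (or randomly drawn) from the normal distribution based on the observed mean and SD of non-missing data by treatment and time point", 500 times. No pooling rule is named.

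The primary analysis (SAP 6.1.1.1) carries the decision rule, "Primary Objective, upper bound of 95% CI of treatment difference" below 0.6, and the per-protocol analysis repeats it. The imputation analysis has no decision rule. Non-responder imputation (SAP 5.3.3 to 5.3.5) applies to binary endpoints only. SAP Section 7 is blacked out, but the SAP version history describes it as concerning the open-label phase.

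**The concern.** A sensitivity analysis should relax the assumption behind the primary analysis. This one tightens it. The MMRM lets missingness depend on observed Week 36 values and covariates. The planned draw treats missingness as unrelated to outcome within arm and visit.

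Outcome-related missingness is plausible by design. Flare that rescue cannot control leads to discontinuation (Protocol 6.3), and rescue for more than 10 consecutive days leads to withdrawal (Protocol 7.23). SAP Appendix 1.2 can then remove the evidence: "observations will be excluded from visit windows if the data was collected more than 7 days off study drug", and where several values share a window, "the value closest to the targeted day will be used as the observation for that week". A routine Day +84 visit therefore displaces a flare visit on Day +110. A withdrawal visit from Randomization Day +127 can supply a Week 48 value only within the 7-day limit.

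If monotherapy subjects are lost more often, or do worse once lost, ignoring them moves the estimate toward non-inferiority. Agreement between imputation and MMRM would then look like confirmation when both carry the same bias.

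**Working it through.** **1. The plan's own figure.** Inputs from Protocol 9.1: SD 1.4, margin 0.6, two-sided 5%, power 90%. Allocation is 1:1.

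n per arm = 2 × (1.960 + 1.282)² × 1.4² / 0.6² = 114.4, rounded up to 115 (230 in total). The noncentral t version gives 116 per arm, 232 in total, with power 90.15%. The stated 232 reproduces with 1.4 as the per-subject SD of change, and it is used that way below.

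**2. What the draw does.** In one arm, let p be the share missing, m the observed mean and m + δ the mean of the missing subjects.

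- Expected filled-in mean: (1 − p)m + pm = m.
- Mean of all subjects: m + pδ.
- Bias of monotherapy minus combination: −(p_mono·δ_mono − p_combo·δ_combo).

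**3. Size.** The documents state no double-blind dropout rate and no post-withdrawal shift, so these are assumptions: 116 per arm, true all-subject difference 0.60, the same shift δ in both arms. Closed form in whole subjects: (a) −(12 − 6)/116 × 1.2 = −0.062; (b) −(17 − 6)/116 × 1.5 = −0.142; (c) 0; (d) +0.142.

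Simulation: 1,500 trials per setting; two-visit unstructured MMRM with the SAP 5.2.2 terms; Week 36/48 correlation 0.5; correlation of change with the Week 24 value −0.3; 20% prior biologic use; half of withdrawers with a Week 36 value that carries the shift; 10 imputation draws per trial.

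| Setting | Missing mono/combo | δ | Planned imputation | MMRM | Imputation − MMRM |
|---|---|---|---|---|---|
| (a) | 10%/5% | 1.2 | 0.538 | 0.552 | −0.0145 |
| (b) | 15%/5% | 1.5 | 0.452 | 0.489 | −0.0365 |
| (c) | 10%/10% | 1.5 | 0.602 | 0.602 | −0.0003 |
| (d) | 5%/15% | 1.5 | 0.747 | 0.711 | +0.0352 |

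Monte Carlo SE of the last column is 0.0006 to 0.0009. The planned imputation matched the observed-case difference to within 0.003 throughout.

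**4. Effect of the visit-window rules.**

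- If 25% or 50% of withdrawers have a Week 48-window value, the last column becomes −0.010 or −0.007 in (a), and −0.026 or −0.016 in (b).
- If the Week 36 values that remain are all pre-flare, imputation and MMRM give 0.536 and 0.537 in (a), and 0.450 and 0.451 in (b). They agree to within 0.001 while both lie 0.06 to 0.15 below 0.60.

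**5. A separate, harsher simulation** (200 trials, 100 imputations, correlation 0.6, no difference among completers, half of the shift visible at Week 36). With 20%/10% missing and a 2-unit shift, the all-subject difference was 0.20, observed-case and imputed differences were both 0.002, and MMRM gave 0.065. The upper limit fell below 0.6 in 58% of trials with full data and in 84.5% with the imputation.

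**6. What a tipping delta would show.** Assumed observed difference 0.1.

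- 10%/5% missing (104 and 110 observed): SE = 1.4 × √(1/104 + 1/110) = 0.1915. Half-width = 1.971 × 0.1915 = 0.37745. Tipping delta = (0.6 − 0.1 − 0.37745)/(12/116) = 0.12255/0.10345 = 1.18. Simulated, allowing for SE growth: 1.14 (10th to 90th percentile 0.93 to 1.37).
- 15%/5% (99 and 110 observed): closed form 0.80; simulated 0.78 (0.63 to 0.93).

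The planned imputation gives upper limits of 0.476 and 0.481 in these two cases, almost the same. At an observed difference of 0.2 with 10%/5%, the planned limit is 0.578 and the tipping delta about 0.22.

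**The case against.** **The quoted rule does little by itself.** It adds −0.015 or −0.037 against a margin of 0.6, nothing in (c), and the opposite sign in (d). The protocol promises different methods, not a missing-not-at-random analysis. This stands, and it limits the weight of the point: the larger loss is the analysis that is absent.

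**Dropout is visible elsewhere.** Low disease activity and remission by DAS28-4(ESR) at Week 48 are reported with dropouts as non-responders and as observed cases (SAP 6.2.4, 6.2.5), and discontinuations are summarised (SAP 6.6.2). This is true, but none of it bears on the 0.6 margin for the mean change.

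**The displacement route is narrow.** A Week 36 visit displaces a flare visit only for withdrawals between about Day +84 and Day +126, which is 42/168 = 25% of the phase. An earlier flare visit is kept, and a later one can supply Week 48, both subject to the 7-day limit. The pre-flare setting is therefore a bound, not an expectation.

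**A delta on monotherapy alone runs in one direction.** It cannot represent (c) or (d). That is accepted: it stresses the claim in the direction that would overturn it.

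**The tipping values depend on the baseline correlation.** The illustration assumes none between change and the Week 24 value. A re-run with −0.3 raised them from 1.14 to 1.26, from 0.79 to 0.92, and from 0.21 (0.00 to 0.46) to 0.37 (0.16 to 0.62). The figures should be read with that spread.

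**Equality with observed cases holds only in expectation.** After baseline adjustment, single-trial gaps had an SD of 0.010 to 0.018.

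**Conclusion.** The point holds. The one missing-data sensitivity analysis of the primary endpoint rests on a stronger assumption than the analysis it is meant to support, and no planned analysis of that endpoint departs from missing at random. In settings (a) to (d), the imputation rule itself shifts the estimate by at most about 0.04 DAS28 units relative to the MMRM. The shared bias that it cannot reveal is 0.06 to 0.15 in (a) and (b) when only pre-flare Week 36 values remain. Its direction depends on which arm loses more subjects and how much worse they are. All dropout rates, shifts and correlations are assumed. The primary decision rule and the trial's error rate are not affected, so this should be corrected but does not invalidate the primary analysis.

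**What to change.** Replace the marginal draw in SAP 5.3 and 6.1.1.2.2 with text such as:

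> Missing DAS28-4(ESR) values will be imputed by regression within treatment arm, conditional on prior bDMARD use, Week 24 DAS28-4(ESR) and the Week 36 analysis-window value selected under Appendix 1.2 where observed (imputed sequentially where not), with parameters drawn. The Section 5.2.2 model will be fitted to each of 500 datasets and the results combined by Rubin's rules. A constant delta will be added to imputed monotherapy Week 48 values in steps of 0.1 from 0 until the upper 95% limit reaches 0.6 (stopping at 3.0 if it does not), and that delta will be reported.

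The delta series is the essential part. When only pre-flare Week 36 values remain, conditional imputation with delta 0 gives the same 0.537 and 0.451 as the MMRM.

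The cost is SAP wording and modest programming, with no new visits or data and no change to the primary analysis. The amendment should be made before unblinding. The sensitivity result may be less favourable than the one now planned, and whether the reported delta is plausible will need clinical judgement.
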